Methods: A proof of action repeated-measures study will be conducted in which healthy men and women (N=15) will be recruited to perform a series of balance and gait measures before using the foot device for a week and after the week of use. The following functional tasks will be performed at each time point: static balance on force plates (two-legged stance, one-legged stance and tandem stance), walking gait measures on an instrumented treadmill (at a preferred speed and a standardized speed) and walking measures on a pressure-sensor filled gait mat. For balance, the center of mass displacement, the variation about the displacement and the speed of the displacement will be calculated during post-processing. For gait, the ankle, knee and hip joint moments and joint excursion kinematics in the sagittal plane of motion will be calculated. The peak ground reaction force, the rate of impact loading and the impulses will be calculated during post-processing. A repeated measures analysis of variance will be used to determine whether significant improvements in the functional outcomes occurred. The one-week change scores in the functional task outcomes will be calculated, and effect sizes of the foot

device on the key functional variables will be determined using Cohen's *d*. Significance will be established at $p < 0.05$.

Application: The findings from this study will improve our understanding of foot device impact on functional performance in people without pre-existing conditions, and will help us create effect sizes for subsequent larger trials.

Introduction

The human foot is the initial point of contact between the body and the environment, and is a critical point to provide sensory information to the central nervous system during dynamic and static tasks (Nurse et al. 2005). The specialized mechanoreceptors of the plantar surface of the foot influence balance, dynamic stability and motion correction strategies. Thus, cutaneous stimulation of the nerves in the foot can dramatically change the motion of the lower extremity. For example, during walking and running, stimulation of the foot nerves (through varied experimental methods) can directly impact α -motorneuron output to the leg musculature (Nurse et al. 2005; Zehr et al. 1997). This output alters the kinematics of motion during gait.

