We seek to expand the understanding and application of the foot device concept to healthy people for injury prevention and performance enhancement. We will determine whether a different design of foot device can improve static balance and gait parameters. Medicine trends are moving toward self-management of healthy movement and preventative strategies to injury. More evidence is needed to determine whether the type of foot device we will test here has potential to improve balance, posture and stability – all of which promote healthy movement and reduce injury risk over the long-term. Here, a proof of action study will be performed to determine the effect size of the foot device use on functional task outcomes of balance and gait in healthy people.

Specific Aims

The Specific Aims of this study are to determine the effect of a foot device after one week of acclimation and use on functional variables of balance and gait. We will test the following hypotheses using the following specific aims:

1) *Determine the effect of an experimental foot device on static balance and center of mass displacement (sway) during standing.*

Hypothesis: Compared to the initial baseline measures, static balance will be improved as shown by reductions in the displacement of the center of mass, speed of motion of the center of mass and less trunk sway. We hypothesize that improvements in balance and sway will occur in two-legged stance, single-legged stance and in tandem stance.

2) *Determine the effect of an experimental foot device on walking gait temporalspatial parameters, ground reaction force patterns and joint forces, and relative foot pressure patterns.*

Hypothesis 2a: After one week, participants will demonstrate improvements in temporal spatial parameters (gait speed, stride width, swing time and single support time) compared to initial baseline measures. We also hypothesize that the rate of impact loading will be lower after one week of use.

Hypothesis 2b: We hypothesize that there will be a shift in foot pressure patterns from the typical pattern to that of pressures that indicate transfer of body weight over the heel, lateral metatarsals and hallux.

Methods

Study Design: This is a repeated-measures study in which participants will serve as their own control. Balance and gait measures will be collected during an initial visit and after one week of using the experimental foot device.

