Participants: Healthy men and women (N=15) will be enrolled into the study. Participants must match all the following criteria to be enrolled:

Inclusion:

- Healthy men and women aged 18 to 40 years
- Willing to maintain current level of physical activity during the study period of a week (no increase or decrease of activity level).

Exclusion Criteria:

- Moderate or severe obesity (body mass index $\geq 35\text{kg/m}^2$)
- Known diagnosis of cardiovascular, orthopaedic, or neurological conditions, uncontrolled diabetes, or any condition that impacts normal walking ability
- Any current ankle, knee, hip or low back pain
- Currently using any knee or ankle brace on a regular basis for joint pains
- Severe back pain, prior spinal fusion or spinal deformity that would affect gait
- Major cardiac or pulmonary conditions and any orthopedic limitation that precludes their ability to independently walk for 10 minutes or longer
- Any major orthopedic injury within the prior 12 months

Recruitment and Informed Consent:

Participants will be recruited from the Gainesville area using flyers, online web ads and word of mouth. If interested, the potential participants will call or email the study team. The study coordinator will then explain the study in detail using the informed consent document as the basis of the discussion, and answer any questions from the participant. Participants can take the consent document to review the information carefully. If the individual does agree to pursue the study, written signatures on the informed consent will then be obtained. The participant will be given a copy of the informed consent document after it is signed and dated. Participants are free to withdraw from the study at any time. The protocol and consent documents identify the research team's obligations to the participant and the participant's obligations to the study while he or she is a participant.

Study Schedule:

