Because there are no directly comparable data from which to construct a matched sample size estimate, we have used the study with the closest match in aims and population (Hamlyn et al. 2012). For the matched pairs design, this study would require a sample size of 14 people to achieve a power of 80% and a level of significance of 5% (two sided), for detecting a mean of the differences of 17 cm² of postural sway area between pairs, assuming the standard deviation of the differences to be 20 cm².

Analysis for the Specific Aims:

Descriptive statistics (means and standard deviations for continuous variables, frequencies and percents for categorical variables) will be calculated on all study variables and demographics. Normality of the data will first be confirmed using Shapiro-Wilk tests.

Aim 1: Determine the effect of an experimental foot device on static balance and center of mass displacement (sway) during standing. We will use repeated measures analysis of variance (ANOVA) to determine whether significant improvements in the functional outcomes occurred. The dependent variables will be the key functional task outcomes for balance (center of mass displacement, variability of displacement and area, and the peak speed of displacement) and the independent variable will be time (initial assessment, week one). Covariates to the models will be body weight and sex. The one-week change scores in the functional task outcomes will be calculated, and effect sizes of the foot device will be determined using Cohen's *d*. For these described statistical tests an α level of 0.05 will be established as significant.

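### Cohen's d from 15 people is meant to inform later trials but has no small-sample correction; on average it runs about 3% to 6% high, depending on an SD the plan does not name

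*Combined protocol and SAP*

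**What the plan says.** The Abstract (Application) says the findings "will help us create effect sizes for subsequent larger trials", and the Introduction closes by saying that "a proof of action study will be performed to determine the effect size of the foot device use". The effect size is therefore a declared product of the study.

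The design is a single group seen twice: "This is a repeated-measures study in which participants will serve as their own control". On numbers, "Healthy men and women (N=15) will be enrolled into the study".

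Under Analysis for the Specific Aims, Aims 1 and 2 use the same sentence: "The one-week change scores in the functional task outcomes will be calculated", and "effect sizes of the foot device will be determined using" Cohen's d. The Abstract (Methods) and the closing Statistics description also name Cohen's d. None of these four places says which SD goes in the denominator, mentions a small-sample correction, or plans a confidence interval for d.

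**The concern.** Cohen's d divides a mean change by an estimated SD. In a small sample the reciprocal of that SD is too large on average, so d is biased away from zero by a known factor. The factor is set by the degrees of freedom of the SD. The bias is separate from the imprecision of d: random error differs in direction from study to study, but this bias always makes an effect look larger.

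At stake is the accuracy of the figure handed to the next trial. The bias affects every d in both aims, and for a true improvement it favours the device. The p-values are untouched, because the repeated-measures tests do not use d.

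**Working it through.** **Inputs.** N = 15 (Methods, Participants); paired design (Study Design); mean difference 17 cm², SD of differences 20 cm², 80% power, two-sided 5%, n = 14 (Statistics, Sample size). The documents give neither the between-visit correlation nor a dropout rate, so both are varied below.

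**The plan's own figure.** The Sample size section states its target as "detecting a mean of the differences of 17 cm² of postural sway area between pairs" and arrives at 14 people. The standardised effect is 17/20 = 0.85. For a paired t-test with the noncentral t distribution, n = 13 gives power 0.803, n = 14 gives 0.836 and n = 15 gives 0.864. The stated 14 is within one of the smallest adequate n. That calculation divides by the SD of the differences.

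**Bias when d uses the SD of change or the baseline SD.** Under normality, the average d is the true effect divided by J(df), where J(df) = Γ(df/2) / [√(df/2) × Γ((df−1)/2)].

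- 15 completers, df = 14: J = 720 / (2.6458 × 287.885) = 0.9453, so 1/J = 1.058, a bias of +5.8%. The usual approximation 1 − 3/(4 × 14 − 1) gives 0.9455.
- 14 completers, df = 13: J = 0.9410, bias +6.3%.
- 13 completers, df = 12: J = 0.9359, bias +6.8%.

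At df = 14, a true 0.85 averages 0.899 and a true 0.50 averages 0.529.

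**Bias when d uses the SD pooled over both visits.** The bias now depends on the between-visit correlation, which is assumed here. Simulation with 15 completers gives:

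| Assumed correlation | Bias of d |
|---|---|
| 0 | +2.8% |
| 0.5 | +3.4% |
| 0.8 | +4.6% |
| 0.95 | +5.4% |

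**Bias against noise.** With the SD of change and a true effect of 0.85, the bias is 0.899 − 0.85 = 0.049 and the SD of d is 0.335. The ratio is 0.147, between one-sixth and one-seventh. At a true 0.50 it is 0.029/0.299, about one-tenth. The 95% interval around an observed d of 0.85 is about 0.24 to 1.43.

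**Effect of correcting.** Hedges' g = J × d. At a true 0.85 its SD is 0.9453 × 0.335 = 0.317 and its bias is zero, so its root-mean-square error is 0.317. For d it is √(0.335² + 0.049²) = 0.338. The correction removes the bias and lowers the total error.

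**The case against.** The strongest objection concerns consequences. Required sample size goes as 1/d², and J² = 0.894, so a reader might infer that later trials would be about 11% too small, with about 75% power instead of 80%. That holds only for a trial sized on exactly the average d. It describes neither the typical nor the average later trial. At a true 0.85:

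- The median observed d is 0.867, so the median planned N is (0.85/0.867)² = 0.96 of the need, about 4% short.
- d exceeds the truth only 52% of the time.
- The mean planned N, restricted to d above 0.1, is about 1.5 times the need, because small observed values of d produce very large trials.
- Using g moves the median planned N to 0.9615/0.8936 = 1.076 of the need, about 8% over.

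So g is the better estimate of the effect, but it does not by itself give better-sized trials. The middle half of planned N runs from 0.60 to 1.62 times the need with d, and the correction barely narrows that spread. The Abstract also says only that the findings will help provide effect sizes. It does not say that raw d will go straight into a sample-size formula. This part of the objection stands in full.

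Two further points stand in part. The standardiser is not named, so 5.8% is conditional: it is the top of the range for 15 completers. And the plan is silent on correction rather than ruling it out. But a statistic named in four places with no adjustment is fairly read as plain d, and an intended correction should be stated.

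**Conclusion.** The point holds as a minor one. Plain Cohen's d from this study overstates the true standardised effect on average:

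- by 5.8% with the SD of change or the baseline SD and 15 completers (6.3% with 14);
- by about 3% to 5.5% with the SD pooled over both visits, for an assumed between-visit correlation of 0 to 0.95.

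This assumes approximately normal data and no correction applied. The study's own tests and its sample size of 14 are unaffected, and the documents support no claim of a fixed shortfall in later trials. The undefined standardiser and the missing interval matter more to a later trialist than the bias itself. They also have to be settled first, because the correction needs a df.

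**What to change.** In the Abstract (Methods) and in Aims 1 and 2:

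1. Name the standardiser. The SD of the one-week change matches the Sample size section and has df = completers − 1.
2. For each continuous outcome report Hedges' g, that is d × J(df), or d × [1 − 3/(4 × df − 1)], with its 95% confidence interval. The shift in peak-pressure location is tested by chi-square and is outside this change.
3. State that g and its interval are the figures for planning later trials, so that the uncertainty is carried forward with the estimate.

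The closing Statistics description is written in the past tense. There the change means giving g and its interval for the results already calculated.

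The cost is one multiplication and one interval per outcome, with no new data or visits. Reported effect sizes become about 3% to 6% smaller.

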slightly unstable. Adjusting to the slight instability might initially feel uncomfortable for some people when they first wear the foot device. This discomfort is expected to improve over time as the participant becomes comfortable wearing them each day. A second anticipated discomfort is the development of mild muscle soreness in the lower extremities from wearing the foot device. As occurs with the start of any new shoe or shoe device where muscles engage in unaccustomed activity, muscle soreness may develop. This may appear in the muscles of the feet, lower leg, upper leg or gluteal muscles. This soreness is transient and is expected to dissipate within 48-72 hours.

With any treadmill or walking tests, there is the very small possibility of injury. We take all precautions to reduce this risk of falling or injury by familiarizing the participant with the treadmill, coaching them through all the processes of the treadmill use and having spotters next to the treadmill.

Informed Consent. Written informed consent will be obtained after explanation to subjects about all procedures and time commitments. The study coordinator will explain to prospective participants the purpose, methods and extent of the study. Potential participants will be asked to read the informed consent form and to ask questions. The form will be written in simple, easy-to-understand language. We require the coordinator to review all key aspects of the study verbally. They will then question potential participants to ascertain whether they have understood the information. A copy of the signed and dated consent form will be given to participants, and the original document will be placed in subjects' individual study files, which will be stored in a locked, secure location in the OSMI.

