Data Safety and Monitoring Plan. Although the risk for an untoward event occurring due to participation in the study is extremely low, we will put all data safety and monitoring procedures into place. A Data and Safety Monitoring Plan (DSMP) will be implemented to ensure the safety of all participants involved in the study and to ensure the validity and integrity of the data. The study team will monitor all aspects of safety. The Study Coordinator will meet monthly to review all Serious, Unexpected and On-site adverse events and will make recommendations to the PI and Co-investigators. Study safety personnel will be notified of all Serious and on-site events within 24 hrs of initial confirmation. The PI will complete an Event notification and Evaluation form which will be reviewed by the IRB. A summary of non-serious events will be reported to the PI and IRB. A structured safety monitoring system will be established in order to both assure real-time participant care and unbiased monitoring of adverse outcomes. For ongoing participant safety, events will be assessed by the PI, physician, and Co-investigators to determine if they are Serious, Unexpected or On-site, as defined below. If so, an event evaluation form will be completed that will include a description of the event, a classification of seriousness, assessment of potential relationship to the study, assessment of need for change in the consent or the study activities, a summary of known prior health issues, event outcome

and a classification of the main organ system involved. The classification of potential relationship to the intervention is as follows:

Definite	Temporal pattern + Known or expected AE response pattern
Probable	Temporal pattern + Known or expected AE response pattern + Could not be explained by participant's clinical state
Possible	Temporal pattern + Known or expected AE response pattern + Could have been produced by a number of other factors
Unknown	Relationship for which no evaluation can be made.
Not related	AE for which sufficient information exists to indicate that the cause is unrelated to the study intervention

The study PI and Co-investigators will notify the IRB of any serious adverse events that result in death or on site events that result in medical care within 24 hrs of being made aware of the serious adverse event.

Participant Compensation for Time and Travel:

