All statistics were performed on SPSS v 25.0. Descriptive statistics were performed on participant characteristics and opinions of orthotics on foot motion and health (means and standard deviations or % of the group). Repeated measures analysis of variance were used to determine whether significant improvements in the main functional outcomes (temporalspatial parameters of gait, ground reaction forces, loading rate and joint moments, foot pressure patterns, balance assessments [amount of center of mass sway in antero-posterior and medial-lateral directions and velocities of sway in different directions) occurred over time point (baseline, week 1). Effect sizes of the foot device on the key functional variables was determined using Cohen's d . Safety measures of lower extremity muscle soreness and pain were reported as means for each day of the study. Significance was established in advance for all tests at $p<0.05$.

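### Felt instability is the first device discomfort named, yet neither it nor non-painful trips, ankle turns and falls during home wear are actively solicited

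*Combined protocol and SAP*

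**What the plan says.** Under Possible Discomforts and Risks (Foot Device and Study Measures), the combined protocol and SAP says the device may feel a little unstable and goes on: "Adjusting to the slight instability might initially feel uncomfortable for some people when they first wear the foot device". It then predicts the course: "This discomfort is expected to improve over time as the participant becomes comfortable wearing them each day". Soreness is placed after it: "A second anticipated discomfort is the development of mild muscle soreness in the lower extremities from wearing the foot device".

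The Statistics description at the end of the document names the safety data to be analysed: "Safety measures of lower extremity muscle soreness and pain were reported as means for each day of the study".

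The Data Safety and Monitoring Plan provides the general route for adverse events. It says "The Study Coordinator will meet monthly to review all Serious, Unexpected and On-site adverse events", and also "A summary of non-serious events will be reported to the PI and IRB". It promises definitions of those three event categories, but what follows is a scale for relatedness to the intervention.

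Under Foot Device and Prescription for Use, the device is worn in the participant's own shoes between the two visits, with daily wear time rising over the week.

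**The concern.** Of the two device discomforts named, the second is followed day by day and the first is not followed at all. The device is being tested for its effect on balance in healthy people, with injury prevention as part of the rationale. Unsteadiness while wearing it is therefore the unwanted effect closest to the claim under study.

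Two things are at stake. First, the stated expectation that the instability improves cannot be checked, because nothing records it over the week. Second, a stumble, turned ankle or fall that leaves no pain reaches the record only if the participant volunteers it. The study could then report lower sway in the laboratory with soreness and pain as its only analysed safety data, and a reader could not tell whether unsteadiness in use was absent or simply not asked about. The results are meant to inform larger trials, so the omission could carry forward.

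**Working it through.** The plan gives no figure on this point to reproduce. Its sample size was built on sway area and does not enter here. The check is a comparison of sections, followed by arithmetic on scale.

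**1. What is measured, and where**

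- *Study Measurements* lists history and covariates, height and weight, balance on force plates, treadmill gait and gait-mat measures. It has no rating of unsteadiness and no question on trips, ankle turns or falls.
- *Analysis for the Specific Aims* covers balance and gait outcomes only.
- *Statistics description* adds daily soreness and pain, and participants' opinions of orthotics. The opinion items are not listed, so they cannot be counted as covering unsteadiness.
- *Force-plate sway* does not fill the gap. It is an efficacy outcome taken at two laboratory visits, not a record of what is felt or what happens during wear between them.

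**2. Which events the existing routes would catch**

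| Event | Route in the documents |
|---|---|
| Ankle turn or fall at home that hurts | Should show in the daily pain measure |
| Fall during a laboratory stance or treadmill test | On-site event under the monitoring plan |
| Home trip, turn or fall without pain | Non-serious summary, if volunteered |
| Felt unsteadiness, day by day | No stated measure; could be volunteered |

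The gap is the last two rows. The monitoring plan describes review and reporting. It does not say that participants are asked about events at home.

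**3. Exposure** (Foot Device and Prescription for Use: one hour on each of days one and two, then one hour more each day until day seven)

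- Day seven included: 1 + 1 + 2 + 3 + 4 + 5 + 6 = 22 hours per person; 15 × 22 = 330 person-hours.
- Day seven excluded: 1 + 1 + 2 + 3 + 4 + 5 = 16 hours per person; 15 × 16 = 240 person-hours.

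**4. What 15 participants could show, even with every event captured** (N = 15 from Participants)

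The documents give no event rate, so the per-person risk p over the week is an assumption, shown across a range. The chance of at least one participant with an event is 1 − (1 − p)^15:

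| Assumed p | Expected participants (15p) | Chance of at least one |
|---|---|---|
| 1% | 0.15 | 1 − 0.99^15 = 14% |
| 5% | 0.75 | 1 − 0.95^15 = 54% |
| 10% | 1.5 | 1 − 0.90^15 = 79% |
| 20% | 3.0 | 1 − 0.80^15 = 96% |

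If no events are seen, the one-sided 95% upper limit solves (1 − p)^15 = 0.05, so p = 1 − 0.05^(1/15) = 18.1%.

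**The case against.** The strongest reply is the monitoring plan. The study team undertakes to monitor safety in general, and non-serious events are summarised for the PI and the IRB. A reader might infer from the Statistics description that soreness and pain are the only safety data collected and that home falls would go unrecorded. The documents do not support that. A volunteered home fall has a route without being serious, on-site or unexpected, and a painful ankle turn should appear in the daily pain data.

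A reader might also take the text to identify a fall hazard from wearing the device. It does not: it calls the instability a discomfort and mentions falling only for treadmill and walking tests, where it says "We take all precautions to reduce this risk of falling or injury by familiarizing the participant with the treadmill". The link from felt instability to trips and falls is an inference, though a reasonable one. Because those precautions concern the treadmill, one might further argue that the balance stances are unprotected. But a fall there would be an on-site event and so would be reviewed; how the stances are supervised is a procedural matter outside this point.

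Three further replies have weight. The documents describe the risk as minimal, and the participants are healthy adults aged 18 to 40. The Statistics description is short and may not list every safety item, and consent pages are not in the file, so an instruction to report home events may exist unseen. Finally, 15 people over one week without a control group will yield little about event rates.

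These replies narrow the point without removing it. None supplies a solicited record of unsteadiness or of painless events, and the low yield is a reason to report descriptively rather than a reason not to ask.

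**Conclusion.** The point holds as a gap in active ascertainment. Felt instability is named first and expected to improve, but no stated measure could show whether it does. Trips, ankle turns and falls without pain during 16 to 22 prescribed hours of wear per person rest on spontaneous reporting, into a system whose event categories are left undefined. Such events may be under-ascertained; the documents do not show that they would be missed altogether.

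The size of any undercount cannot be stated, because the documents give no event rate. Depending on an assumed risk of 1% to 20%, the chance that at least one of 15 participants has an event runs from 14% to 96%, and the conclusion does not rest on any value in that range. It rests on two assumptions: that the visible text describes the safety data in full, and that the daily means reflect a rating made each day. The primary sway analysis is unaffected. This is an inexpensive improvement, not a flaw that undermines the study.

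**What to change.** Add two items to the daily soreness and pain rating:

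- felt unsteadiness while wearing the device; and
- any trip, turned ankle or fall that day (yes/no, and whether the device was on or off).

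Ask the second item again at the one-week visit, for the whole week.

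In the analysis text, state that the number of participants with any event and the day-by-day course of unsteadiness will be reported descriptively beside the sway results. Add that zero events among 15 would still be compatible with a true per-person risk up to about 18% (one-sided 95% limit). Device-on and device-off events should be listed without a formal comparison, because hours on and off differ. Supplying the event definitions that the monitoring plan promises would complete the change.

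The cost is two short daily items, one question at an existing visit and one descriptive table. It needs no change to sample size or design. The downside is slight participant burden and some reports of trivial stumbles.
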